Therapeutic plasma exchange followed by convalescent plasma transfusion in severe and critically ill COVID-19 patients: A single centre non-randomized controlled trial

trial registration number: NCT04973488

Date: 3 August, 2020

Study design, setting and population

A total of 38 Caucasian patients will be included in the present single center non-randomized controlled trial. All patients included in the study will be adults (>18 years) who present with acute respiratory failure and ARDS, and have positive reverse transcriptase-polymerase chain reaction (RT-PCR) test results for SARS-CoV-2 virus upon hospital admission. ARDS is defined as acute-onset hypoxemia (P/F ratio <300) with >50% bilateral pulmonary opacities on chest imaging within 24-48 h that are not fully explained by congestive heart failure and that require ICU treatment and monitoring. Exclusion criteria are represented by any of the following: Pregnancy, patients with suspected or confirmed pulmonary embolisms and patients with terminal disease, patients < 18 years of age. Patients enrolled in the study will be divided equally, non-randomized, into two groups as follows: A treatment group who will benefit of sequential TPE and CVP transfusion in addition to the standard treatment for COVID-19, and a control group who benefit of only standard treatment for COVID-19 (antiretrovirals, corticosteroids, anticoagulants and antibiotics if deemed necessary) according to hospital protocols. All patients will provide written informed consent immediately after admission into the ICU regarding all the procedures performed during hospitalization, including the treatment scheme applied in the present study and the use of the resulting data in scientific research publications, with the assurance that they will remain anonymous. In cases where obtaining informed consent from the patients will not be possible due to their critical medical condition, a legal representative will be informed and provide written consent. The trial was approved by the Ethics Committee of 'Pius Brinzeu' Emergency Clinical County Hospital Timisoara (approval no. 91/03.08.2020).

Study protocol

The blood type of the patients will be determined immediately upon being admitted to the ICU. In the treatment group, a dual lumen, 14 French, dialysis catheter will be used for vascular access, by placing it in the femoral vein under echographic guidance. A single TPE session will be performed on the Infomed HF 440 machine (Infomed SA), with a plasma/blood separation ratio of 20%, using 40 ml/kg fresh frozen plasma as the substitute. The circuit will be anticoagulated with unfractionated heparin during the procedure. Upon completion of the TPE session, each patient from the treatment group will be transfused with 500 ml of ABO compatible CVP. Patients will be carefully monitored

during both the TPE session and the CVP transfusion, and also after the procedures, in order to treat emerging complications.

[figure not shown]
Patients from the treatment and control groups will receive standard treatment for COVID-19 according to hospital protocols, consisting of corticosteroids, antiretrovirals, anticoagulants and antibiotics if deemed necessary. Patients from both groups will be anticoagulated with subcutaneous nadroparine (Fraxiparine; Aspen Pharma Trading) in therapeutic dosage, once every 12 h, adjusted according to bodyweight (≤ 70 kg: 3,800 Anti-Xa IU; >70 kg: 5,700 Anti-Xa IU). Patients from the treatment and control groups will receive corticosteroids in the form of 16 mg dexamethasone (Dexamethason; Krka) divided into 2 doses, daily. Antiretrovirals administered will be the ones in the hospital COVID-19 protocol lopinavir/ritonavir (Kaletra; Hetero Labs, Ltd.), 300 mg b.i.d. and remdesivir (Veklury; Gilead Sciences), 200 mg loading dose, then 100 mg o.d. for 5 days. Antimalarial drugs will also be used, in the form of hydroxychloroquine (Plaquenil; Sanofi-Aventis), 400 mg b.i.d. loading dose, then 200 mg b.i.d. Upon clinical (fever, chills, sweats or aspect/quantity of bronchial secretions) and paraclinical (leucocytosis, CRP or cultures) findings of infection, empiric antibiotics will be started, until de-escalation following culture results will be possible. Patients will be intensively monitored, and daily clinical and laboratory data will be collected during the ICU stay. Outcomes monitored will be survival at 30 days, oxygenation (P/F ratio) (normal ratio >300) and inflammatory markers [CRP (normal range 0-5 mg/l), LDH (normal range 135-225 U/l) and ferritin (normal range 30-400 μ g/l)] at the 7-day follow-up, as assessed using ASTRUP analyses and blood tests.

Statistical analysis plan

Statistical data will be analysed using GraphPad Prism 8 (GraphPad Software, Inc.) and IBM SPSS Statistics 20 (IBM Corp.). The category variables will be characterized by value and percentage. Continuous variables will be presented as mean (\pm standard deviation) and median (interquartile range). Data distribution testing will be performed using the Shapiro-Wilk test. The numerical variables will be compared with the t-test for independent samples or the Mann-Whitney U test, depending on the type of distribution of the variables. The χ^2 test (or Fisher's exact test) will be used for the nominal variables. The Kaplan-Meyer method with the log-rank (Mantel-Cox) test will be applied to evaluate the primary endpoint. Cox regression will be utilized to determine hazard ratio of the treatment group. All statistical tests will be calculated with 2 tails and $P<0.05$ will be considered to indicate a statistically significant difference.

Local Ethics Committee Decision regarding Scientific Research in Human Subjects

SPITALUL CLINIC JUDEȚEAN DE URGENȚĂ „PIUS BRÎNZEU” TIMIȘOARA

• [name]
• Cod fiscal 4663448 • Telefon [name] • [contact]
• e-mail: [contact] • www.hosptm.ro

91/03.08.2020

DECIZIA COMISIEI LOCALE DE ETICA PENTRU CERCETARE STIINTIFICA A SPITALULUI CLINIC JUDETEAN DE URGENȚA TIMIȘOARA

Va comunicam avizarea din punct de vedere etic a studiului clinic cu titlul:

"Therapeutic plasma exchange succeeded by convalescent plasma transfusion in critically ill Covid -19 patients - a single center non- randomized controlled trial"

Departamentul in care se desfosoara: Compartiment ATI – Covid, Spitalul Clinic Judetean de Urgenta "Pius Brinzeu" Timisoara, Sectia ATI Covid, Spitalul Clinic Municipal Lugoj

Persoane responsabile pentru desfasurarea studiului clinic: Conducator de doctorat- [name]. [name], Laborator Clinic Central, doctorand- dr. [name], Clinica ATI - Spitalul Clinic Judetean de Urgenta "Pius Brinzeu" Timisoara.

Studiul se va realiza in baza consintamantului informat semnat de catre pacient/ reprezentant autorizat al pacientului la internarea in spital, consintamant care cuprinde si investigatiile imagistice care se efectueaza pe perioada internarii. Se va asigura anonimizarea totala a investigatiilor, pentru a nu permite sub nici o forma identificarea pacientilor.

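### Does the second hospital named in the ethics decision call for a site term in the analysis of a trial described as single centre?

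*Combined protocol and SAP*

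**What the plan says.** The title and the section on study design, setting and population both describe one centre: "A total of 38 Caucasian patients will be included in the present single center non-randomized controlled trial". That section also gives the allocation, "Patients enrolled in the study will be divided equally, non-randomized, into two groups as follows", with no rule for who enters which group.

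The local ethics committee decision carries the approval number that the protocol cites (91/03.08.2020). Its line for the department of conduct names two units. The first is "Compartiment ATI – Covid, Spitalul Clinic Judetean de Urgenta", the COVID intensive care compartment of the Timisoara county hospital. The second is "Sectia ATI Covid, Spitalul Clinic Municipal Lugoj", the COVID intensive care ward of the Lugoj municipal hospital. The study title quoted in the same decision still reads "a single center non- randomized controlled trial".

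The statistical analysis plan evaluates the primary endpoint by Kaplan-Meier and log-rank, and adds: "Cox regression will be utilized to determine hazard ratio of the treatment group". It names no stratum and no covariate. The plan does not say which hospital's patients enter which group.

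**The concern.** The protocol and its own approval letter disagree about where the trial takes place. In a randomised trial that would matter little, because chance would spread hospitals over the groups. Here allocation is not random and no rule is given, so nothing prevents the treated patients from coming mainly from one hospital and the controls mainly from the other.

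An unadjusted log-rank test would then credit treatment with whatever mortality difference exists between the hospitals. The extreme case is all treated patients in one hospital and all controls in the other; hospital and treatment could then not be separated by any analysis. With 38 patients and a survival endpoint, it is reasonable to ask whether the plan should name hospital as a stratum.

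**Working it through.** **Step 1: which reading do the documents support?**

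For one enrolling centre:
- the protocol title and the design sentence;
- the title quoted in the ethics decision;
- the approval, which the protocol cites from the Timisoara hospital only;
- the responsible-persons line of the decision, which names no hospital but Timisoara;
- the antiviral regimen, which the study protocol section takes from the hospital's COVID-19 protocol, in the singular.

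For two: the single line listing departments. It may mean that patients enrol at Lugoj, or only that conduct there is permitted. The evidence does not exclude Lugoj, but two enrolling sites is the less supported reading. With one enrolling hospital, the hospital confounding is exactly zero.

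**Step 2: how large would it be if both enrolled?**

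The plan gives no event rate, effect size or power, so it has no figure to reproduce beyond 38/2 = 19 per group. Everything below is illustrative.

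Assumptions: no treatment effect; exponential survival censored at day 30; 50% mortality at 30 days at the geometric mean of the two hospitals' hazards; hospital hazard ratio 1.5; 19 patients from each hospital.

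- Mean hazard: ln 2 / 30 = 0.023105 per day.
- Hospital A: 0.023105 / √1.5 = 0.018865. Hospital B: 0.023105 × √1.5 = 0.028298.
- 30-day mortality, 1 − exp(−30 × hazard): A 0.432, B 0.572.
- Expected days at risk per patient, mortality / hazard: A 22.91, B 20.22.

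Example, with 14 of 19 treated and 5 of 19 controls from A:
- Treated: deaths 14 × 0.4322 + 5 × 0.5721 = 8.91; days 14 × 22.91 + 5 × 20.22 = 421.8; rate 0.02113.
- Control: deaths 5 × 0.4322 + 14 × 0.5721 = 10.17; days 5 × 22.91 + 14 × 20.22 = 397.6; rate 0.02558.
- Apparent rate ratio: 0.02113 / 0.02558 = 0.83, where the truth is 1.

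False-positive rates come from simulating the unstratified two-sided log-rank test at 0.05. Information kept is the mean stratified variance over the mean unstratified variance.

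| From A, treated / control | Apparent ratio, HR 1.5 | (HR 1.3 to 2.0) | False positives, HR 1.5 | (HR 1.3 to 2.0) | Information kept if stratified |
|---|---|---|---|---|---|
| 12 / 7 | 0.90 | 0.93 to 0.84 | 5% | 5% to 6% | 92% |
| 14 / 5 | 0.83 | 0.88 to 0.72 | 7% | 6% to 11% | 77% |
| 17 / 2 | 0.73 | 0.81 to 0.58 | 11% | 8% to 22% | 37% |
| 19 / 0 | 0.67 | 0.77 to 0.50 | 14% | 9% to 32% | none |

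Assuming 30% or 70% mortality instead moves the ratios by less than 0.01.

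**Step 3: drop the equal-contribution assumption.**

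Every row above takes 19 patients from each hospital, which leaves room for the most extreme imbalance. Suppose instead that Lugoj supplied only 4 of the 38, all controls and all at the higher hazard. At hospital HR 1.5 the treated rate is 0.018865. The controls have 15 × 0.4322 + 4 × 0.5721 = 8.77 deaths over 15 × 22.91 + 4 × 20.22 = 424.5 days, a rate of 0.02066. The ratio is 0.91, and the false-positive rate is between 5% and 6% for hospital HR 1.3 to 2.0. With 6 of 38, all controls, the ratio is 0.87 at HR 1.5 and the false-positive rate is about 5% to 7.5% over the same range. The estimate shifts somewhat; the test hardly does.

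**Step 4: what would a hospital stratum buy?**

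It restores the false-positive rate to 5% to 6% whenever both hospitals feed both groups. As the last column shows, it is cheap where little correction is needed, costly where the bias is large, and useless at a complete split.

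**The case for a change.** The strongest case for acting is that the contradiction is a matter of text, not of assumption. Both statements are legible and current, and a reader cannot tell for certain where patients enrol. A complete split by hospital cannot be repaired afterwards, so the time to rule it out is before enrolment, and a sentence naming the enrolling hospital costs nothing. Larger assumed differences also give larger distortion. With 14/5 and 30-day mortality of 40% v 60%, the false-positive rate is 8.7%; at 30% v 70% it is 21.5%. With a complete split and 30% v 70%, it is 73%.

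What stands: the inconsistency is real, and a report of the trial should say which hospital or hospitals enrolled into each group. If that turned out to be both, hospital should be tabulated by group and a hospital-stratified analysis shown as a sensitivity check. An analyst can do both from data already held.

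What does not stand is the step from a list of places to a defect in the analysis. The committee is repeating the submitted title, so its letter is weak evidence on either side. The protocol also lists the same background drugs for both groups ("Patients from the treatment and control groups will receive standard treatment for COVID-19 according to hospital protocols", followed by named agents), which narrows what could differ between hospitals to case mix and other care; on these the documents are silent. The high false-positive rates need both a marked split and a strong hospital difference, neither of which has support in the text. The wider weakness, non-random allocation with no rule and no named covariate, is the same with one hospital or two, and a hospital term would not remove it.

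**Conclusion.** No change to the plan is needed. Followed as written, the trial enrols at one centre and hospital cannot confound it; the list of two units is then a clerical mismatch with no effect on any result.

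Under the two-site reading, the apparent ratio in the primary comparison ("Outcomes monitored will be survival at 30 days") would be 0.90 to 0.67 at a hospital hazard ratio of 1.5, and the false-positive rate 5% to 14%, from a 12/7 to a complete split. These figures rest on an assumed hospital hazard ratio, mortality, split and equal hospital contributions, none of which the documents give. The effect on the test is small unless the imbalance or the hospital difference is marked.

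The remedies for that reading are not clear gains. Drawing both groups from each hospital needs plasma exchange and convalescent plasma at both. A mandatory stratum in 38 patients gives up 23% of the information at 14/5 (100 − 77) and 63% at 17/2 (100 − 37). Leaving hospital out of a plan that declares one centre is therefore reasonable, and naming the enrolling hospital is a detail for the trial report. Documentary evidence that patients were enrolled at both hospitals would change this conclusion.

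### Entry criteria do not restrict both groups to patients who could undergo plasma exchange and convalescent plasma, so patients unfit for the procedure can gather in the control group

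*Combined protocol and SAP*

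**What the plan says.** Study design, setting and population enrols "adults (>18 years) who present with acute respiratory failure and ARDS, and have positive reverse transcriptase-polymerase chain reaction (RT-PCR) test results". On exclusions it states: "Exclusion criteria are represented by any of the following: Pregnancy, patients with suspected or confirmed pulmonary embolisms and patients with terminal disease, patients < 18". None of these criteria concerns fitness for the intervention.

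The same section states "Patients enrolled in the study will be divided equally, non-randomized, into two groups as follows". It gives no rule for who goes where. The experimental arm is described by what its members get: "A treatment group who will benefit of sequential TPE and CVP transfusion in addition to the standard treatment for COVID-19".

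The Study protocol section then sets requirements that fall on treated patients only: a 14 French dialysis catheter in the femoral vein, an extracorporeal circuit, 40 ml/kg of fresh frozen plasma as replacement fluid and, once the session is complete, "each patient from the treatment group will be transfused with 500 ml of ABO compatible CVP". On the circuit it adds: "The circuit will be anticoagulated with unfractionated heparin during the procedure". No rule covers a patient placed in the treatment group who cannot start or finish the procedure.

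The Statistical analysis plan evaluates the primary endpoint by Kaplan-Meier with a log-rank test and obtains the hazard ratio by Cox regression. It names no stratification factor, covariate or analysis set.

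**The concern.** The two groups are drawn from one entry list, but one of them must also be able to undergo an invasive procedure. A patient too unstable for the circuit, without usable femoral access, or with a previous reaction to plasma meets every criterion as written. With allocation left open, the natural place for such a patient is the control group. The treatment group would then hold only patients fit for the procedure, and the control group a mixture of fit and unfit.

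If unfitness goes with a higher risk of death, as is plausible for instability, control mortality rises for reasons unrelated to treatment, and the log-rank test and hazard ratio credit the difference to TPE plus plasma. A covariate in the Cox model would be a weak remedy, because an obstacle that fully rules out the procedure has no treated counterpart and the model must extrapolate. If instead such a patient is placed in the treatment group, the entry list has not prevented it.

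**Working it through.** **Inputs from the documents.** "A total of 38 Caucasian patients will be included in the present single center non-randomized controlled trial". Equal division gives 38 / 2 = 19 per group. The survival outcome is at 30 days, and tests are two-sided at 0.05. The plan gives no mortality rate, no share of patients unfit for TPE, and no derivation of the 38, so there is no planned figure to reproduce.

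**Which obstacles apply to treatment only.** The requirements, set against what controls receive:

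- Femoral dialysis catheter: treatment only.
- Tolerance of the extracorporeal circuit: treatment only.
- Tolerance of donor plasma: treatment only.
- A compatible convalescent unit: treatment only, but a matter of supply that need not relate to prognosis.
- Anticoagulation: not treatment only. The Study protocol section plans nadroparine, described as therapeutic dosage, for both groups, so a contraindication to anticoagulation conflicts with either regimen.
- Consent: not a route into control. Every patient or representative consents to the treatment scheme.

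**Assumptions.** There is no true treatment effect. Let k be the number of unfit controls, m0 the 30-day mortality of fit patients and m1 that of unfit patients. All treated patients are fit.

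- Control mortality: mc = [(19 − k) × m0 + k × m1] / 19
- Spurious difference: mc − m0 = k × (m1 − m0) / 19
- Apparent hazard ratio (ratio of cumulative hazards at day 30): ln(1 − m0) / ln(1 − mc)

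**Worked case,** m0 = 0.40, m1 = 0.70, k = 4: mc = (15 × 0.40 + 4 × 0.70) / 19 = 8.8 / 19 = 0.463. The difference is 4 × 0.30 / 19 = 6.3 points, or 1.2 expected extra control deaths. The apparent HR is ln(0.600) / ln(0.537) = 0.82.

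The last column comes from simulation: 19 v 19, exponential survival times, censoring at day 30, 4,000 trials per row. It shows how often the log-rank test is significant in favour of treatment, against a nominal 2.5%.

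| m0 | m1 | k | Control mortality | Difference (points) | Apparent HR | Falsely favours treatment |
|---|---|---|---|---|---|---|
| 0.40 | 0.70 | 2 | 0.432 | 3.2 | 0.90 | 4.1% |
| 0.40 | 0.70 | 4 | 0.463 | 6.3 | 0.82 | 6.0% |
| 0.40 | 0.70 | 6 | 0.495 | 9.5 | 0.75 | 8.2% |
| 0.40 | 0.90 | 2 | 0.453 | 5.3 | 0.85 | 5.3% |
| 0.40 | 0.90 | 4 | 0.505 | 10.5 | 0.73 | 10.1% |
| 0.40 | 0.90 | 6 | 0.558 | 15.8 | 0.63 | 15.7% |
| 0.50 | 0.30 | 4 | 0.458 | −4.2 | 1.13 | 1.3% |

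**Range.** With m0 from 0.30 to 0.60, m1 of 0.70 or 0.90, and k from 2 to 8, the apparent HR runs from 0.97 (negligible) to 0.44 (large). If m1 = m0 the difference is zero for any k. With k = 0 the HR is 1.00 and the two-sided rejection rate was 4.5% to 5.9% across runs.

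**The case against.** The direction is not documented. The plan gives no mortality by fitness and no share of unfit patients. A purely logistic obstacle, such as no compatible unit, produces no bias if it is unrelated to prognosis, and unfit patients with a better outlook would push the result the other way. Clinicians might also choose the sickest patients for TPE, which could offset or outweigh this mechanism. All of this stands, and it limits the claim to a likely direction and an unknown size.

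A reader might infer that unfit patients can only end up as controls. The documents do not say so: with no assignment rule or analysis set, such a patient could be treated anyway, moved or dropped.

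A reader might also take bleeding or heparin intolerance as the leading examples. They are not obstacles for treatment alone, given the anticoagulation planned for both groups. Instability, vascular access and plasma intolerance remain.

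Nor is an entry rule the only remedy. Matching, or restricting the analysis to patients who could have been treated, would also work if fitness were recorded at baseline in both groups. The plan does not ask for that record. Where instability is a matter of degree, ordinary adjustment could also help, but no covariates are named.

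Finally, one may call this part of the wider problem of non-random allocation. It is related, but it has its own specific and cheap remedy.

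**Conclusion.** The concern holds in a limited form. It is certain that the entry criteria do not confine both groups to patients able to undergo the procedure, and that nothing in the allocation or analysis prevents unfit patients from gathering in control. That this favours treatment is likely but not established: it requires that such patients are in fact placed in control and that they die more often within 30 days. A firm statement that the plan biases survival towards treatment would go beyond the documents.

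The size is unknown. On the assumed 40% and 70% mortality, 2 to 6 unfit controls correspond to 0.6 to 1.8 expected extra control deaths (k × 0.30). That is modest in count, but enough to raise the one-directional false-positive rate from 2.5% to between about 4% and 8%. The gap should be closed because the remedy is cheap.

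**What to change.** In Study design, setting and population:

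- Add one entry criterion for both groups, documented at a common time point before the group is chosen: the treating team confirms that the patient could undergo the procedures described in the Study protocol section. The investigators set the clinical list of contraindications; the statistical requirement is that the same list applies to everyone.
- Record lack of a compatible convalescent plasma unit separately, and do not use it as an exclusion. Such patients may be informative controls, because their obstacle need not relate to prognosis.
- Keep a log of patients screened out on this criterion, with the reason.
- State how patients are assigned to a group.

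In the Statistical analysis plan, state that survival is analysed by assigned group from that common time point, whether or not the procedure was completed.

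The cost is a short checklist at ICU admission, where blood type is already determined, slightly slower enrolment, and a conclusion limited to patients able to undergo TPE. The change removes this mechanism only. Selection among fit patients, and other confounding from non-random allocation, remain.

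### Does leaving the survival time origin and analysis set unstated undermine the 30-day comparison of the two groups?

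*Combined protocol and SAP*

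**What the plan says.** The combined document's opening section (study design, setting and population) gives the size, "A total of 38 Caucasian patients will be included in the present single center non-randomized controlled trial", and the split, "Patients enrolled in the study will be divided equally, non-randomized, into two groups as follows". Dividing 38 equally gives 19 per group. The same section has consent obtained as soon as the patient reaches the ICU, or from a legal representative where the patient cannot give it.

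The study protocol section then describes what is done to a group that already exists. It begins "In the treatment group, a dual lumen, 14 French, dialysis catheter will be used for vascular access", specifies one exchange session "with a plasma/blood separation ratio of 20%, using 40 ml/kg fresh frozen plasma as the substitute", and ends "Upon completion of the TPE session, each patient from the treatment group will be transfused with 500 ml of ABO compatible CVP". It gives no interval from ICU admission to the session.

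On outcomes, the same section says "Outcomes monitored will be survival at 30 days, oxygenation (P/F ratio" and adds inflammatory markers at a 7-day follow-up. The statistical analysis plan says "The Kaplan-Meyer method with the log-rank (Mantel-Cox) test will be applied to evaluate the primary endpoint" and "Cox regression will be utilized to determine hazard ratio of the treatment group". It does not name the primary endpoint. Thirty-day survival is inferred because it is the only listed outcome suited to a time-to-event method.

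Nothing readable gives the start of the 30 days, an analysis set, or a rule for a treatment-group patient who does not complete both procedures. One figure in the study protocol section is not shown and five passages were removed, so a timeline may exist elsewhere.

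**The concern.** A log-rank test and a Cox model need a start of follow-up that means the same thing in both groups, and a group label that does not depend on later survival. A randomised trial has an obvious candidate for both in its randomisation date. This trial has none. Convalescent plasma follows the exchange, so a patient can count as treated only by living long enough to receive both. If early deaths were dropped from the treatment group, or replaced to keep 19 and 19, that group would be credited with survival time that its members had to live through to be counted. If treated patients were timed from plasma and controls from admission, the hazard ratio could move either way.

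With 19 per group, one patient can matter. Suppose 7 of 19 treated and 13 of 19 control patients die, one of the treated on day 1. The log-rank p-value is 0.073 with everyone kept, 0.038 with that patient dropped, and 0.027 with that patient replaced by a survivor. The fear is that two analysts could follow the same plan and report different verdicts.

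**Working it through.** **Reading the text.** The design section takes patients who are enrolled and divides them. The protocol section applies the catheter, exchange and plasma to the treatment group so formed. The analysis plan asks for the hazard ratio of that same named group. Assignment therefore comes before treatment, and group membership does not depend on surviving to treatment. Analysed as assigned from a common origin, the comparison has no immortal-time bias at any delay. Completers-only analysis, replacement, and separate clocks for the two groups appear nowhere; each would be a rule added by the analyst.

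**Inputs for sizing a departure.** From the documents: 19 per group (38/2), 30 days of follow-up, two-sided 5% level. Assumed, because the documents give no event rate or delay: 50% 30-day mortality, clock from ICU admission, completion at 6 hours, 1 day or 3 days, and Weibull hazards with shape k = 1.5 (rising), 1 (constant) or 0.7 (front-loaded). There is no stated power calculation to reproduce.

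**Chance of an early death.** Per patient, p = 1 − exp[−ln 2 × (t/30)^k]. For at least one in 19, P = 1 − (1 − p)^19. At 1 day with k = 1, p = 1 − exp(−0.693/30) = 2.3%, and P = 36%.

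**If completers only were analysed, with no true effect.** Hazard ratios come from a Cox fit to very large simulated groups. Disagreement is the share of all simulated 19-v-19 trials in which the as-assigned and completers-only log-rank tests fall on opposite sides of 0.05. Each cell gives k = 1.5 / 1 / 0.7.

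| Delay to completion | At least one early death in 19 | Completers-only HR | Verdicts disagree, all trials |
|---|---|---|---|
| 6 hours | 1 / 10 / 37% | 1.00 / 0.99 / 0.95 | 0.03 / 0.25 / 1.2% |
| 1 day | 8 / 36 / 70% | 0.99 / 0.96 / 0.88 | 0.2 / 1.1 / 3.2% |
| 3 days | 34 / 73 / 93% | 0.96 / 0.87 / 0.75 | 1.1 / 3.5 / 7.6% |

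False positives favouring treatment (nominal 2.5%) are 2.5 to 2.7% as assigned. For completers only they are 2.7/3.3/4.6% at 1 day and 3.2/4.7/8.1% at 3 days.

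**Which delay applies.** The session itself is short. Time in minutes = 40 × kg / (0.20 × blood flow in ml/min). With assumed weights of 60 to 100 kg and flows of 100 to 200 ml/min, the limits are 2,400/40 = 60 minutes and 4,000/20 = 200 minutes. Any long delay would have to come from the wait beforehand, on which the documents are silent.

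**How special the one-patient illustration is.** With its spacing of deaths (one treated death on day 1, the other treated deaths evenly over days 4.1 to 27.1, control deaths evenly over days 2.5 to 28.5), I took control deaths from 8 to 16 and every lower treated count from 2 upward, 90 combinations in all. Dropping the early death crosses 0.05 in 9, one for each control count. In those 9 the as-assigned p-value lies between 0.057 and 0.107.

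**Cost of the natural reading.** Keeping early deaths dilutes a real effect. With a true hazard ratio of 0.50 after completion, the as-assigned value is about 0.50/0.52/0.56 at 1 day and 0.52/0.56/0.62 at 3 days.

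**The case for a change.** The strongest reply is that the plan permits the harmless analysis without requiring it. Without a randomisation date, day 0 has to be chosen. Consent may come after ICU admission when a representative signs. An equal split of 38 and the statement that every treatment-group patient is transfused could tempt a team to replace an early death. Dropping such a patient once the outcome is known moves the result towards treatment.

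The consequence is also larger if the treatment works. With a true hazard ratio of 0.50 after completion, the two analyses would disagree over all trials in about 0.1/1.1/4.4% at 6 hours, 0.8/4.2/11.5% at 1 day and 4.0/12.2/23.2% at 3 days. Restricted to trials with at least one early death, the range at 1 to 3 days is 11 to 25%.

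The silence is real, and so are the direction of the bias and the arithmetic. What does not stand is the step from silence to a faulty plan. Every adverse figure needs an analyst to depart from the group formed at enrolment, and the larger ones also need a wait of a day or more, or deaths concentrated at the start. The documents support neither assumption. A randomised trial would likewise have to state how it treats non-completers, so this gap is not peculiar to the design.

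**Conclusion.** The concern does not call for a change. The plan omits a detail and contains no wrong rule, and the ordinary way to fill it is the unbiased one: keep each patient in the group formed at enrolment and count 30 days from one event common to both groups. Writing that down would record the default analysis.

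If an analyst did restrict to completers, the no-effect hazard ratio would range from about 1.00 to 0.75 and the verdict would change in about 0.03% to 7.6% of all trials, according to delay and hazard shape. One patient's handling decides significance only when the as-assigned p-value is already a little above 0.05.

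These sizes rest on 50% mortality and delays that the documents do not give. The conclusion itself rests on reading assignment as preceding treatment, which the order of the text supports. Confounding from non-random assignment is a separate matter, which no choice of time origin removes.
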